#### 4.4.4.2 Biomarker Research

Biomarkers of the capacity for anticancer response are an important objective across the field of immunotherapy.

Specimen collection at 4 time points will accommodate testing in coordination with other data sets. The plan will include:

*FIGURE 4: TYPES AND TIMES OF CORRELATIVE SPECIMENS*

|                                                   |                                               |
|---------------------------------------------------|-----------------------------------------------|
| Baseline
(pretreatment or B1D1)                | Archival tumor

Leukocytes

Serum |
| After 4 doses pembrolizumab/before IL-2
(B2W2) | Leukocytes

Serum                       |
| After 10x IL-2                                    | Leukocytes                                    |

|                |            |
|----------------|------------|
| (B2W4)         | Serum      |
| After all IL-2 | Leukocytes |
| (B4W1)         | Serum      |

#### 4.5 Combination rationale

IL-2 and kidney cancer: The susceptibility of kidney cancer to IL-2 treatment has been a cornerstone of the cancer immunotherapy, but with limitations that define a ceiling on its overall the kidney cancer and generalizable oncologic impacts. Dimensions of this are limitations on how frequently complete responses are observed, and how many patients can tolerate a standard schedule, and how to build on (the current label) standard schedule, and how to have more centers available to patients. On the other hand, the achievement of unmaintained durable responses at 10-20+ years is not a limitation, but an opportunity and a standard for other anticancer therapies to aspire. The standard high-dose IL-2 inpatient treatment has associated high frequency side effects that must be managed in an experienced setting; not necessarily severe or debilitating, but requiring a base of experience for hospital staff and physician. Building on over 20 years' experience, many functional IL-2 administration centers with a steady (narrow) stream of patients having IL-2 administration and responses. These are tabulated in the Prometheus sponsored PROCLAIM registry (Wong et al. *J Immunother Cancer*. 2014; 2: 20). As practical issues of immunotherapy response determinants are developed, driven by responses and durable responses, a wider use of immunotherapy – cell therapies, checkpoints, or cytokines – can be anticipated.

Checkpoint inhibition and kidney cancer: Cancer immunotherapy with checkpoint inhibitors has demonstrated potential for clinical impact in many cancers, including in kidney cancer. With regard to clinical experiences in PD-1 inhibition, trials with nivolumab monotherapy (Choueiri ASCO 2014 #5012), and with ipilimumab + nivolumab (Hammers ASCO 2014 #4504) are examples of patients with kidney cancer with observed major regression after treatment including PD-1 checkpoint inhibition without other therapies. VEGF + checkpoint inhibition. Our case report observation of RCC regression on IL-2 after prior nonresponse to nivolumab (Brayer 2014) is a pointed example that immunotherapy responses to different drugs do not all represent responses within the same small subset of patients. Use of more, different immunotherapies may be a way to on a bigger fraction of the incident patient population. Registrational size phase III studies of nivolumab after VEGFR-TKI progression and of ipilimumab + nivolumab as initial therapy are ongoing, with trial hypotheses to impact on median (50th percentile) survival. The relative potential of pembrolizumab vs other PD-1 pathway antibody drugs such as nivolumab, MEDI-4376, MPLD3280a, particularly in

patients with tumors that bear markers of immune susceptibility (such as lymphocytic infiltrates, or 12-chemokine signature, or PD-L1 expression) remains to be developed for kidney cancer therapy. Combination therapies overlapping checkpoint inhibition with VEGF treatments, just in kidney cancer, include axitinib and pembrolizumab (open at Moffitt), as well as nivolumab, and ipilimumab. Many other disease states are under study, including with approved VEGF pathway drugs.

Checkpoints and cytokines, together: Every lymphocyte that is an effector of checkpoint inhibition response has IL-2 receptor on it (NK cells, T cells, B-cells all have IL-2 receptors). Conversely, every IL-2 activated lymphocyte, whether bearing low & intermediate affinity receptor (CD25 [IL2Ra] or CD 122 & 132 [IL2R $\beta$  & IL2R $\gamma$ ]) or high affinity receptor (CD25, CD122, CD132) has potential to have been modulated by PD-1 pathway, or to be later affected either directly through its own PD-1 receptors, or indirectly through the changed behavior of other lymphocytes bearing PD-1 receptor. As described by in our recent AACR poster (Choueiri *et al* 2014) PD-1 inhibition in kidney cancer patients induces two changes that are encouraging for synergy – more intratumoral lymphocytes, and more IL-2 receptor ( $\beta$ chain).

The core common feature of these immune therapies is that the lymphocytes bear receptors of both of these drugs and the intratumoral resistance mechanisms remain to be completely defined. One common feature, for example, may be that tumors with no discernable penetration by leukocytes are resistant. Another may be that patients with a high burden of tolerance promoting myeloid derived suppressor cells will not reach a response. How will NK and T cells respond to IL-2 in the context of PD-1 inhibition? That is the central biological question. That biological question is fundamental to the key clinical questions: Will more tumors regress? Will immunologic side effects be amplified in the short term? Will immunologic side effects be amplified in the long term? Both drugs have limitations—IL-2 with short term toxicity, pembrolizumab with unestablished durability of responses, potential for late autoimmune toxicity, and both with limited overall response frequency and incomplete algorithms for patient selection. However, this study will work towards finding a regimen that is feasible, and ultimately raising rates of durable, unmaintained remissions the central goal of oncolytic therapeutics.

The rationale for the pembrolizumab and IL-2 combination in this study is to achieve safely a cooperative anticancer effect of both drugs. This is to use high dose, bolus IL-2 (so as to still have ligation of low affinity IL-2R), on a schedule that we had developed to accommodate having a relatively more stable overall dose delivery (5-in-a-row doses x four 3-day admissions instead of 14-in-a-row with two 6 day admissions; Finkelstein 2010), on a schedule that is reliable, and usually ends each course without a critical IL-2 dosing limitation. This now will be done in a context of inhibition of PD-1. This development will

have to be done in a measured way, using experienced centers because of the unknowns as far as possible exacerbations of immune-related side effects. If response frequency and dose delivery appear promising, multicenter development will be appealing. In a small series such as this, the potential of each drug to induce a completer response in some patients is acknowledged – this is totally consistent with the rationale of combining these two for the central oncologic goal of increasing the fraction of complete responses. The scope of this study is limited to establishing this as feasible schedule. Efficacy can be measured as progression free survival, major response rate, complete response rate, landmark 1-year survival, or median overall survival, any of which could be fundamental and reasonable components for the rational further development of oncologic therapeutics.

Pharmacodynamic testing of lymphocytes should recapitulate the experiences of the nivolumab RCC treatment trial, as far as altered expression of lymphocytes proteins, and may define a way to understand the processes underlying clinical resistance, to be tested in further future trials.

## 5.1 METHODOLOGY

### 5.2 Entry Criteria

#### 5.2.1 Diagnosis/Condition for Entry into the Trial

Metastatic kidney cancer. Clear cell histology component from primary or metastatic lesion.

#### 5.2.2 Subject Inclusion Criteria

In order to be eligible for participation in this trial, the subject must:

1. Be willing and able to provide written informed consent for the trial.
2. Age over 18 on day of signing informed consent.
3. Have measurable disease based on RECIST 1.1.

[http://ctep.cancer.gov/protocolDevelopment/docs/Recist\\_Guideline.pdf](http://ctep.cancer.gov/protocolDevelopment/docs/Recist_Guideline.pdf)

4. Be willing to provide tissue from a newly obtained or archival tissue, if available.
5. Have a performance status of 0 or 1 on the ECOG Performance Scale.
6. Demonstrate adequate organ function as defined in Table 1.

Table 1 Adequate Organ Function Laboratory Values

| System                                                                                                                                          | Laboratory Value                                                                                                                                                  |
|-------------------------------------------------------------------------------------------------------------------------------------------------|-------------------------------------------------------------------------------------------------------------------------------------------------------------------|
| Hematological                                                                                                                            |                                                                                                                                                                   |
| Absolute neutrophil count (ANC)                                                                                                                 | $\geq 1,500 / \mu\text{L}$                                                                                                                                        |
| Platelets                                                                                                                                       | $\geq 100,000 / \mu\text{L}$                                                                                                                                      |
| Hemoglobin                                                                                                                                      | $\geq 9 \text{ g/dL}$ or $\geq 5.6 \text{ mmol/L}$ without transfusion or EPO dependency (within 7 days of assessment)                                            |
| Renal                                                                                                                                    |                                                                                                                                                                   |
| Serum creatinine OR
Measured or calculated a creatinine clearance
(GFR can also be used in place of creatinine or CrCl) | $\leq 1.5 \times \text{upper limit of normal (ULN)}$ OR
$\geq 60 \text{ mL/min}$ for subject with creatinine levels $> 1.5 \times$ institutional ULN    |
| Hepatic                                                                                                                                  |                                                                                                                                                                   |
| Serum total bilirubin                                                                                                                           | $\leq 1.5 \times \text{ULN}$ OR
Direct bilirubin $\leq \text{ULN}$ for subjects with total bilirubin levels $> 1.5 \text{ ULN}$                         |
| AST (SGOT) and ALT (SGPT)                                                                                                                       | $\leq 2.5 \times \text{ULN}$ OR
$\leq 5 \times \text{ULN}$ for subjects with liver metastases                                                           |
| Albumin                                                                                                                                         | $\geq 2.5 \text{ mg/dL}$                                                                                                                                          |
| Coagulation                                                                                                                              |                                                                                                                                                                   |
| International Normalized Ratio (INR) or Prothrombin Time (PT)                                                                                   | $\leq 1.5 \times \text{ULN}$ unless subject is receiving anticoagulant therapy as long as PT or PTT is within therapeutic range of intended use of anticoagulants |
| Activated Partial Thromboplastin Time (aPTT)                                                                                                    | $\leq 1.5 \times \text{ULN}$ unless subject is receiving anticoagulant therapy as long as PT or PTT is within therapeutic range of intended use of anticoagulants |

aCreatinine clearance should be calculated per institutional standard.

7. Female subjects of childbearing potential must have a negative urine or serum pregnancy within 72 hours prior to receiving the first dose of study medication. If the urine test is positive or cannot be confirmed as negative, a serum pregnancy test will be required.
8. Female subjects of childbearing potential must agree to use 2 methods of birth control or be surgically sterile, or abstain from heterosexual activity for the course of the study through 120 days after the last dose of study medication (Reference Section 5.8.2). Subjects of childbearing potential are those who have not been surgically sterilized or have not been free from menses for  $> 1$  year.
9. Male subjects must agree to use an adequate method of contraception starting with the first dose of study therapy through 120 days after the last dose of study therapy.
10. Cardiac testing with either exercise stress test or thallium stress test, within 3 months of start of the first treatment day. Atrial fibrillation that is rate controlled is allowed. Note – the first treatment day is about 9 weeks before the first IL-2 treatment day. If a cardiologist's evaluation determines that this is superfluous based on other assessments, then this may be omitted.
11. Pulmonary function test is required, within 3 months of start. The treating physician will assess suitability by usual clinical criteria used for IL-2 treatment generally

consistent with the Proleukin™ prescribing information. There is no specific minimum result specified by the protocol

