### 5.8.2 Contraception

Pembrolizumab may have adverse effects on a fetus in utero. Furthermore, it is not known if pembrolizumab has transient adverse effects on the composition of sperm. Non-pregnant, non-breast-feeding women may be enrolled if they are willing to use 2 methods of birth control or are considered highly unlikely to conceive. Highly unlikely to conceive is defined as 1) surgically sterilized, or 2) postmenopausal (a woman who is  $\geq 45$  years of age and has not had menses for greater than 1 year will be considered postmenopausal), or 3) not heterosexually active for the duration of the study. The two birth control methods can be either two barrier methods or a barrier method plus a hormonal method to prevent pregnancy.

Subjects should start using birth control from study Visit 1 throughout the study period up to 120 days after the last dose of study therapy.

The following are considered adequate barrier methods of contraception: diaphragm, condom (by the partner), copper intrauterine device, sponge, or spermicide. Appropriate hormonal contraceptives will include any registered and marketed contraceptive agent that contains an estrogen and/or a progestational agent (including oral, subcutaneous, intrauterine, or intramuscular agents).

Subjects should be informed that taking the study medication may involve unknown risks to the fetus (unborn baby) if pregnancy were to occur during the study. In order to participate in the study they must adhere to the contraception requirement (described above) for the duration of the study and during the follow-up period defined in section 7.2.2-Reporting of Pregnancy and Lactation to the Sponsor and to Merck. If there is any question that a subject will not reliably comply with the requirements for contraception, that subject should not be entered into the study.

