### **5.8.3 Use in Pregnancy**

If a subject inadvertently becomes pregnant while on treatment with pembrolizumab, the subject will immediately be removed from the study. The site will contact the subject at least monthly and document the subject's status until the pregnancy has been completed or terminated. The outcome of the pregnancy will be reported to the Sponsor and to Merck without delay and within 24 hours to the Sponsor and within 2 working days to Merck if the outcome is a serious adverse experience (e.g., death, abortion, congenital anomaly, or other disabling or life-threatening complication to the mother or newborn).

The study investigator will make every effort to obtain permission to follow the outcome of the pregnancy and report the condition of the fetus or newborn to the Sponsor. If a male subject impregnates his female partner the study personnel at the site must be informed immediately and the pregnancy reported to the Sponsor and to Merck and followed as described above and in Section 7.2.2.

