| Directed Physical Examination                                                                                           | x                       |                                | x                        | x   | x   |         | W1                       | W4       | x   |         |                  | x                                           |                                              |                                        |
| Vital Signs and Weight                                                                                                  |                         | x                              | x                        | x   | x   | x       | x                        | x        | x   | x       |                  |                                             |                                              |                                        |
| ECOG Performance Status                                                                                                 | x                       | x                              | x                        |     |     |         | x                        |          |     | x       | x                | x                                           | x                                            | x                                      |
| Laboratory Procedures/Assessments: analysis performed by LOCAL laboratory                                        |                         |                                |                          |     |     |         |                          |          |     |         |                  |                                             |                                              |                                        |
| Pregnancy Test – Urine or Serum β-HCG (only for women of child bearing potential; must be <72 hours before first dose.) |                         |                                | x                        | x   | x   |         | x                        | x        | x   | x       |                  |                                             |                                              |                                        |

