† Perform on women of childbearing potential only. If urine pregnancy results cannot be confirmed as negative, a serum pregnancy test will be required.

‡ If considered standard of care in your region.

Laboratory tests timing and evaluation are described in section 6.1 .

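### Inclusion 8's definition of childbearing potential lacks the age condition of Section 5.8.2, so a small group of women who must use contraception has no required pregnancy test

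*Combined protocol and SAP*

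**What the plan says.** Section 5.2.2 Subject Inclusion Criteria, item 8, defines the term: "Subjects of childbearing potential are those who have not been surgically sterilized or have not been free from menses for" more than 1 year. The same item sets the contraception duty. Women in this group "must agree to use 2 methods of birth control or be surgically sterile, or abstain from heterosexual activity for the course of the study"; the duty runs until 120 days after treatment ends, and the item refers to Section 5.8.2.

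Section 5.8.2 Contraception does not use the term. Women who are neither pregnant nor breast-feeding "may be enrolled if they are willing to use 2 methods of birth control or are considered highly unlikely to conceive". There are three ways to count as unlikely to conceive: surgical sterilization, being postmenopausal, or not being heterosexually active during the study. For the second, a woman of at least 45 "years of age and has not had menses for greater than 1 year will be considered postmenopausal".

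The pregnancy-test rules all depend on item 8's term:

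- Item 7 of the same section: "Female subjects of childbearing potential must have a negative urine or serum pregnancy within 72 hours prior to receiving the first dose".
- The flow chart in Section 6.1, pregnancy-test row: "only for women of child bearing potential; must be <72 hours before first dose".
- The footnote to Table 5 in Section 7.2.1 Laboratory Procedures/Assessments: "Perform on women of childbearing potential only".

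**The concern.** The protocol draws the line between women who might conceive and women who will not in two places, and the lines differ. Item 8 decides who is tested. Section 5.8.2 decides who must use contraception, and by setting an age floor of 45 it declines to treat a year without menses as enough on its own. A woman between the two lines is treated as able to conceive for contraception but not for testing. Section 5.8.2 itself says that pembrolizumab may harm a fetus, so a required negative test before the first dose matters for her.

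Item 8 is also loosely worded: it joins two negatives with 'or'. Most readers will take this as neither sterilized nor free of menses for a year. Read literally, a woman who fails either condition is of childbearing potential, which is a much wider group.

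**Working it through.** The protocol gives no figure to reproduce, so the check sets the rules side by side and then bounds the size.

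**Step 1. Classify women by the two facts in item 8 plus the age condition in 5.8.2.** The 5.8.2 duty means two methods or abstinence.

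| Group | Item 8, neither/nor | Item 8, literal 'or' | 5.8.2 duty |
|---|---|---|---|
| Not sterilized, menses within the past year, any age | Yes, tested | Yes, tested | Yes |
| Not sterilized, no menses for more than 1 year, under 45 | **No, not tested** | Yes, tested | **Yes** |
| Not sterilized, no menses for more than 1 year, 45 or older | No | **Yes, tested, contraception** | **No** |
| Sterilized, still menstruating | No | Tested; the sterilization option meets the contraception duty | No |
| Sterilized, no menses for more than 1 year | No | No | No |

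On the neither/nor reading, the mismatch is in the second row: a 5.8.2 duty with no required test. On the literal reading, no woman with a 5.8.2 duty escapes testing. The excess falls on the third row (tests and contraception) and the fourth (tests only).

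**Step 2. Which reading is meant?** The literal reading would call a sterilized woman who still menstruates of childbearing potential, although 5.8.2 lists sterilization first among the reasons for being unlikely to conceive. That is strained. One phrase points the other way: item 8 offers surgical sterility as an option to women of childbearing potential, which has content only on the literal reading. It may simply be redundant drafting.

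**Step 3. Size on the neither/nor reading.** Section 1.0 gives N = 26. The documents give no sex, age or menopausal mix, so both shares below are assumptions.

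- Women, assumed 25% to 35%: 26 × 0.25 = 6.5 and 26 × 0.35 = 9.1, so take n = 6 to 9.
- Share p of these women in the second row, assumed 1% to 5%.
- Expected number, n × p: 6 × 0.01 = 0.06 to 9 × 0.05 = 0.45.
- Chance of at least one, 1 − (1 − p)^n: 1 − 0.99^6 = 0.059 to 1 − 0.95^9 = 0.370.

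This is the chance of enrolling such a woman, not of missing a pregnancy, which is far smaller.

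**Step 4. Tests involved.** If the extracted columns are aligned, the flow chart marks 3 tests in each pembrolizumab-only block and 4 in each IL-2 block: 2 × 3 + 2 × 4 = 14 over four blocks, including the one before the first dose. Extra pembrolizumab cycles could add to this.

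**Step 5. Timing.** Section 1.0 estimates that enrollment ends in 3/2019, and this version is dated 03/16/2020. If enrollment closed as estimated, testing before the first dose is past. Treatment would be over or nearly so: 36 weeks from 31 March 2019 is 8 December 2019, and the month or two of slack in Section 2.2 runs to early February 2020. The documents do not say whether accrual kept to the estimate.

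**The case against.** The strongest objection is that nobody is told to do incompatible things. A reader might infer that items 7 and 8 contradict 5.8.2. They do not. On the neither/nor reading, item 8 is silent about the woman under 45, and 5.8.2, to which it points, still imposes contraception or abstinence on her. On the literal reading, item 8 merely asks for more than 5.8.2, whose wording ("may be enrolled if they are willing to use 2 methods of birth control or are considered highly unlikely to conceive") does not forbid that. This stands: it is a mismatch.

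A reader might also infer that a pregnant woman could properly be enrolled. The documents do not support that. Exclusion 15 bars pregnant women under any definition, Section 7.2.1.2 has the investigator review every criterion, and 5.8.2 admits only women who are not pregnant. Section 7.2 Trial Procedures allows unscheduled procedures when clinically necessary, and under 5.8.3, "If a subject inadvertently becomes pregnant while on treatment with pembrolizumab, the subject will immediately be removed from the study". These protections are real, but none of them requires a test for the woman in question. The required negative test is in item 7, which turns on item 8's definition.

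Two further objections stand. The literal reading should carry little weight: it is strained, nothing shows that any site applies it, and its only effect is unneeded testing and contraception. The counts also rest on assumed shares, so the range of 6% to 37% shows scale and is not an estimate.

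**Conclusion.** The point holds as a minor wording mismatch with one practical consequence. On the usual reading of item 8, an unsterilized, heterosexually active woman under 45 without menses for more than 1 year must use two methods or abstain but has no required pregnancy test, before treatment or during it. That rests on the text alone.

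The size is very small: probably 0 or 1 patient under the assumed shares, and perhaps no remaining effect if enrollment closed as estimated. A reader might infer from a fault in an eligibility rule that the trial's results are in doubt. They are not: the definition plays no part in the response-rate analysis, sample size, error rates or toxicity boundary, and no efficacy or safety conclusion changes.

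**What to change.** Make two edits to inclusion item 8 at the next amendment:

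1. Replace the last sentence with: *A subject is of childbearing potential if she is neither surgically sterilized nor postmenopausal as defined in Section 5.8.2 (aged 45 or older with no menses for more than 1 year).*
2. Delete the surgical-sterility option from the first sentence. Once sterilized women are outside the definition, it applies to nobody.

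Section 5.8.2, item 7, the flow chart row and the Table 5 footnote can stay as they are. In the table under Step 1, only the first two rows then count as of childbearing potential, and these are exactly the rows with a 5.8.2 duty. A woman who abstains remains subject to testing and meets the contraception duty by abstaining.

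The cost is one short edit and the testing of a few women under 45 who in fact cannot conceive. If any site now applies the literal wording, the edit also ends required testing of unsterilized postmenopausal women of 45 or older and of sterilized women who still menstruate, in line with 5.8.2.
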